Appendix I: Serum Creatinine Clearance Calculation

According to the National Institute of Diabetes and Digestive and Kidney Diseases (NIDDK; <https://www.niddk.nih.gov/health-information/professionals/clinical-tools-patient-management/kidney-disease/laboratory-evaluation/glomerular-filtration-rate-calculators/ckd-epi-adults-conventional-units>) in adults, the most widely-used equations for estimating glomerular filtration rate (GFR) from serum creatinine are the Chronic Kidney Disease Epidemiology Collaboration (CKD-EPI) equation and the isotope dilution mass spectrometry (IDMS) traceable Modification of Diet in Renal Disease (MDRD) Study equation.

This CKD-EPI equation calculator should be used when S_{cr} is reported in mg/dL. This equation is recommended when eGFR values above 60 mL/min/1.73 m² are desired.

$$GFR = 141 \times \min(S_{cr}/\kappa, 1)^\alpha \times \max(S_{cr}/\kappa, 1)^{-1.209} \times 0.993^{\text{Age}} \times 1.018 \text{ [if female]} \times 1.159 \text{ [if African American]}$$

Where:

- S_{cr} is serum creatinine in mg/dL,
- κ is 0.7 for females and 0.9 for males,
- α is -0.329 for females and -0.411 for males,
- min indicates the minimum of S_{cr}/κ or 1, and
- max indicates the maximum of S_{cr}/κ or 1.

The equation does not require weight because the results are reported normalized to 1.73 m² BSA, which is an accepted average adult surface area.

The GFR estimate should be calculated by CKD-EPI equation using the Merck Manual Calculator:

<https://www.merckmanuals.com/professional/multimedia/clinical-calculator/glomerular-filtration-rate-estimate-by-ckd-epi-equation>

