The Phase 2 objectives will apply to the investigation of DAY101 as monotherapy and in combination with other therapies. Additional objectives may be specified according to the relevant sub-protocol.

Primary Objective:

To evaluate the efficacy of DAY101 by RECIST version 1.1 or appropriate tumor response criteria as a monotherapy or in combination with other therapies

Secondary Objectives:

- To assess the safety and tolerability of DAY101 as monotherapy or in combination with other therapies.
- To assess additional efficacy parameters of DAY101 as monotherapy or in combination with other therapies.
- To characterize the tumor responses observed with DAY101 as monotherapy or in combination with other targeted therapies.
- To characterize the PK profile of DAY101 in combination with other therapies
- To characterize the PD effects of DAY101 as monotherapy or in combination with other therapies.
- To determine the relationship between PK and PD of DAY101 in combination with other therapies.

Exploratory Objectives:

- [REDACTED]
- To evaluate the genomic profile of archival tumor or fresh tumor biopsies and ctDNA from patients who will be treated with DAY101 as monotherapy or in combination with other therapies.
- To characterize pathway modulation and/or genomic alterations from tumor biopsies.
- To characterize genomic alterations in ctDNA.
- [REDACTED]
- [REDACTED]

STUDY DESIGN:

This is a Phase 1b/2, multi-center, open-label, umbrella study of patients 12 years of age with recurrent or progressive solid tumors with alterations in the key proteins of the RAS/RAF/MEK/ERK pathway, which will be referred to as the mitogen-activated protein kinase (MAPK) pathway. Patients with these alterations will be identified through molecular assays as routinely performed at Clinical Laboratory Improvement Amendments of 1988 (CLIA) or other similarly certified laboratories.

Based on the identified alterations in the key proteins of the MAPK pathway, patients may be offered the opportunity to participate in one or more sub-protocols within this umbrella study of DAY101 as monotherapy or in combination with other therapies. Enrollment will be based on the specific eligibility criteria described in each sub-protocol.

Study DAY101-102 (master study) and sub-protocol consist of a screening period, a treatment period, a safety follow-up period, and a long-term follow-up period where survival, status and subsequent anticancer therapies are collected.

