6.17. Laboratory Tests

For pediatric/adolescent patients (aged < 18 years), blood volumes drawn will be minimized, in accordance with the European Commission (EC)'s recommendations, "Ethical considerations for clinical trials on medicinal products conducted with the pediatric population" (2008) and "Ethical considerations for clinical trials on medicinal products conducted with minors" (2017).

Routine laboratory tests will be performed locally. Special assessments such as PK will be performed centrally or as individually indicated. Additional information on the handling and processing of PK samples is provided in the separate Laboratory Manual.

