6.17.3. Serum Chemistries

Serum chemistries (non-fasting) should include assessment of the following: alkaline phosphatase, albumin, alanine aminotransferase (ALT), AST, CPK, blood urea nitrogen (BUN), creatinine, creatinine clearance, glucose, lactate dehydrogenase, total and direct bilirubin, total protein, sodium, serum calcium (corrected calcium), phosphate, magnesium, and potassium. For calculated creatinine clearance, see Appendix I.

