### **2.3.7. Safety Assessments**

Safety assessments include clinical laboratory tests, vital signs, physical examinations, ophthalmologic exam, visual acuity, clinical adverse events, 12-lead resting ECG (performed in triplicate), and ECHO/MUGA. These assessments will be conducted according to Table 2: Schedule of Events.

Clinical laboratory tests include:

- Hematology: hemoglobin, hematocrit, red blood cell count, white blood cell count with differential (neutrophils [count and percentage], lymphocytes, monocytes, eosinophils, basophils), and platelet count
- Chemistry: alkaline phosphatase, albumin, ALT, AST, CPK, BUN, creatinine, creatinine clearance, glucose, lactate dehydrogenase, total and direct bilirubin, total protein, sodium, serum calcium, phosphate, magnesium, and potassium.
- Coagulation: Prothrombin Time (PT)/International Normalized Ratio (INR), and activated prothrombin time (PTT).

- Thyroid Function Tests: thyroid stimulating hormone (TSH), and free tetraiodothyronine (free T4), and reflexive triiodothyronine (T3) may be obtained.
- Urine or Serum pregnancy test.

Vital sign measurements include:

- Body temperature
- Heart rate
- Respiratory rate
- Systolic and diastolic blood pressure
- Oxygen saturation

Physical examinations include a review of systems such as extremities, genitourinary, head/ears/eyes/nose/throat, lymph nodes, musculoskeletal, pulmonary, and skin. Any symptoms related to skin discomfort, visual disturbance and cardiopulmonary will also be assessed.

The investigator will evaluate any laboratory abnormalities or other safety assessments for clinical significance, and clinically significant abnormalities will be recorded as adverse events (AEs). Abnormal laboratory findings that result in new or worsening clinical sequelae, require therapy, or adjustment in current therapy will be considered AEs and analyzed according to NCI Common Terminology Criteria for Adverse Events (CTCAE) v5.0.

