## **3.5. Demographics and Baseline Characteristics**

### **3.5.1. Demographics**

The following demographics and baseline characteristics will be summarized by cohort and overall for the Efficacy Analysis Set and Safety Analysis Set.

- Age (years)
- Age group: 12 years to <18 years, >=18 years
- Race
- Ethnicity
- Sex
- Height and weight
- Body Surface Area (BSA)
- Number of prior therapy lines
- BRAF fusion (Yes, No)
- CRAF/RAF1 fusion (Yes, No)
- CRAF/RAF1 amplification (Yes, No)
- ECOG Performance Status
- Tumor types (tissue agnostic cohort)

Demographics and baseline characteristics will be presented in a patient listing.

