### **3.8.4. Clinical Laboratory Evaluation**

The clinical laboratory parameters will be analyzed using the Safety Analysis Set by cohort and overall.

Laboratory values will be assigned toxicity grades when available using the NCI CTCAE version 5.0. Directional shifts in laboratory toxicity grades from baseline to post-baseline highest grade will be tabulated. For analytes without a toxicity grading scale, shift tables will present directional shifts from baseline to above or below the laboratory standard normal range.

All clinical laboratory values will be presented in patient listings. Out of normal range values will be flagged.

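### As written, Appendix I applies an adult kidney-function equation to patients aged 12 to under 18

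*Protocol*

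**What the plan says.** Protocol Section 6.17.3 includes creatinine clearance among the serum chemistries, without an age qualifier, and gives one pointer to the method: "For calculated creatinine clearance, see Appendix I".

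Appendix I cites an adult calculator page and introduces CKD-EPI and MDRD as, "in adults, the most widely-used equations for estimating glomerular filtration rate". It writes out only CKD-EPI. The inputs are serum creatinine, age, sex and race. It explains that weight is not needed because the result is indexed to 1.73 m², which it describes as an average for adults. It ends with "The GFR estimate should be calculated by CKD-EPI equation using the Merck Manual Calculator", and that sentence carries no age limit.

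Protocol Section 3.1 sets the lower age limit at 12 years. SAP Section 3.5.1 carries adolescents as their own baseline category: "Age group: 12 years to <18 years, >=18 years". The laboratory section of the protocol does address patients under 18, but only on sampling: "For pediatric/adolescent patients (aged < 18 years), blood volumes drawn will be minimized".

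The SAP repeats the item in its chemistry list in Section 2.3.7 ("CPK, BUN, creatinine, creatinine clearance, glucose") without a formula. Section 3.8.4 then says: "All clinical laboratory values will be presented in patient listings".

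**The concern.** A required value has one stated method, and the text describes that method in adult terms. A site that follows Section 6.17.3 for a 13-year-old arrives at CKD-EPI. A site that notices the adult framing may choose something else. Adolescent values could then come from an equation not presented as suited to them, or from different equations at different sites, and the listing would not show which.

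The plan treats age differently elsewhere. Performance status uses the Lansky scale under 16 (Section 6.8). Blood pressure has a paediatric measurement rule (Section 6.10) and reference tables by height and age (Appendix H). Adolescent dosing is scaled to body surface (SAP Section 2.2). Kidney function is a laboratory value for which no such provision appears.

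What is at stake is how far an adolescent's creatinine clearance can be trusted when someone reviews that patient's renal safety. The amendment summary says the item was added at a regulator's request for monitoring, so it is meant to be read.

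**Working it through.** The plan states no figure to reproduce. The check is mainly a reading of the text, with one calculation that describes the printed equation.

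**Step 1. Who is sent to Appendix I?** Section 6.17.3 has no age split, so the pointer covers everyone enrolled, from age 12.

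**Step 2. What does Appendix I tell them to do?** It frames the equations as adult in three places: the address of the cited page, the opening sentence, and the explanation of 1.73 m². Its closing instruction is unrestricted. Steps 1 and 2 together put adolescents under CKD-EPI.

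**Step 3. Is there an alternative elsewhere?** The under-18 text in Section 6.17 concerns blood volume only. Appendix J gives a body-surface formula but does not link it to renal function. SAP Sections 2.3.7, 3.3.3.2 and 3.8.4 give no formula. No adolescent method appears in either document.

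**Step 4. How does the printed equation behave between 12 and 17?** With creatinine S in mg/dL and the race factor left out:

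GFR = 141 × min(S/κ, 1)^α × max(S/κ, 1)^(−1.209) × 0.993^age × 1.018 (if female)

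κ is 0.9 and α is −0.411 for males; κ is 0.7 and α is −0.329 for females. Take S = 0.6, which is an assumption, since the documents give no creatinine values. S/κ is then below 1 for both sexes and the max term equals 1.

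| | Age 12 | Age 17 |
|---|---|---|
| Male: 141 × (0.6/0.9)^(−0.411) × 0.993^age | 153.1 | 147.8 |
| Female: 141 × (0.6/0.7)^(−0.329) × 0.993^age × 1.018 | 138.8 | 134.0 |

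Units are mL/min/1.73 m². At any fixed creatinine and for either sex, the ratio of age 17 to age 12 is 0.993^5 = 0.9655, a fall of about 3.5%. Height is not an input, so two adolescents of the same sex, age and creatinine (and the same race factor) get the same value whatever their height. This shows that the equation has no term specific to adolescents. It does not measure the error against true GFR.

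**Step 5. Does the plan expect small patients?** The adolescent dose is 420 mg/m² capped at 600 mg (SAP Section 2.2). The cap is reached at 600/420 = 1.43 m², so the dosing rule provides for patients well below the 1.73 m² reference.

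**Step 6. Where does the value go?** Patient listings are certain. Section 3.8.4 also describes shift tables, by toxicity grade or normal range, per cohort and pooled, but does not name creatinine clearance. No laboratory table is split by age; the 12 to under 18 group is a baseline row, and the efficacy subgroups are sex and CNS tumour (SAP Section 3.2.4). The stopping rules (protocol Section 8.3) and the events of special interest (protocol Appendix G, SAP Section 3.8.3) do not use the value.

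**The case against.** The strongest reply is that Appendix I supplies a single rule for all ages, and that preferring another equation needs outside knowledge. The appendix says where its equations are commonly used. It does not say that CKD-EPI is invalid under 18, and neither document compares equations in adolescents. This stands in part: the documents do not show that any adolescent value would be wrong by a given amount. What they do show is that the protocol's own description of the method does not fit part of its population.

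A second reply is that this is a master protocol. Eligibility, dose modification, toxicity management and schedules sit in the sub-protocols, where an adolescent renal rule may also sit. That is fair, and the repair may then be only a cross-reference. The reference would still be needed, because Section 6.17.3 points to Appendix I alone.

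A third reply is that nothing depends on the value. Serum creatinine is collected separately, no decision rule in the two documents uses the clearance, the number of adolescents is not given, and 102a has ended early. All of this stands, and it fixes the size of the point.

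A reader might go further and infer that adolescents have no method at all. That requires reading the closing sentence of Appendix I as limited to adults, which its wording does not say; the unrestricted reading is the more natural one.

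**Conclusion.** Wrong as written, minor. Taken together, Section 6.17.3 and Appendix I apply an equation framed for adults, indexed to an adult body surface and without height, to patients aged 12 to under 18.

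The effect is confined to one safety-laboratory value in adolescents. The response rate, sample size and error rates are untouched. Two further inferences are not supported. The 3.5% age factor is not a bias estimate, because the documents contain no adolescent reference equation or measured GFR. Nor can an effect on eligibility or dosing be claimed, because no rule in these documents uses the value and the sub-protocols were not available.

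The conclusion rests on two assumptions: that the closing instruction in Appendix I means what it says for every patient sent there, and that no sub-protocol overrides it for adolescents. If a sub-protocol does, what remains is a missing cross-reference.

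**What to change.** In Appendix I, limit the CKD-EPI instruction to patients aged 18 or over. For ages 12 to under 18, name one height-based paediatric eGFR equation, or refer to the sub-protocol if it already has a rule. State which height to use: the nearest one recorded on or before the creatinine date. As an optional tidy-up, label the result as eGFR in mL/min/1.73 m², since that is what the printed equation returns.

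For 102a, which the sponsor ended early (SAP Section 2.2.1), add one SAP line deriving any adolescent values this way from recorded data, or footnote them in the listing with the equation used. The master-protocol wording still matters for any other sub-protocol that relies on it; Section 6.11 names 102b.

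The cost is appendix wording and one extra derivation. No new tests are needed: creatinine is already collected, and SAP Table 2, footnote c, keeps height collection going at later physical examinations for ages 12 to under 18. Because visit timing is redacted, it cannot be confirmed that height and creatinine fall on the same day, which is why the nearest-prior rule should be written down.

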Appendix J: Body Surface Area (BSA) Calculation

Body Surface Area (BSA) will be calculated using the Mosteller Method*:

$$\text{BSA (m}^2\text{)} = (\text{height (cm)} \times \text{weight (kg)})/3600^{\frac{1}{2}}$$

Also expressed as:

$$\text{BSA (m}^2\text{)} = \text{square root of (height (cm) x weight (kg)/3600)}$$

*Mosteller RD. Simplified calculation of body surface area. *N Engl J Med.* 1987;317:1098.

## LIST OF ABBREVIATIONS

Abbreviation	Full Term
AE	Adverse Event
ALT	Alanine Aminotransferase
AST	Aspartate Aminotransferase
ATC	Anatomical Therapeutic Class
BRAF	V-Raf Murine Sarcoma Viral Oncogene Homolog B
BSA	Body Surface Area
BUN	Blood Urea Nitrogen
CI	Confidence Interval
CPK	Creatinine Phosphokinase
CR	Complete Response
CRAF	V-Raf Murine Sarcoma Viral Oncogene Homolog C
CRF	Case Report Form
CT	Computed Tomography
CTCAE	Common Terminology Criteria For Adverse Events
ctDNA	Circulating Tumor DNA
DOR	Duration Of Response
ECG	Electrocardiogram
ECOG	Eastern Cooperative Oncology Group
EOT	End Of Treatment
INR	International Normalized Ratio
LTFU	Long-Term Follow-Up
LVEF	Left Ventricular Ejection Fraction
MAPK	Mitogen-Activated Protein Kinase
MEdDRA	Medical Dictionary For Regulatory Activities
MRI	Magnetic Resonance Imaging
MUGA	Multigated Acquisition Scan
MUGA	Multiple-Gated Acquisition
NCI	National Cancer Institute

Abbreviation	Full Term
ORR	Overall Response Rate
OS	Overall Survival
PD	Pharmacodynamic(S)
PFS	Progression-Free Survival
PK	Pharmacokinetic(S)
PR	Partial Response
PR	Pulse Rate
PT	Preferred Term
PTT	Activated Prothrombin Time
RAF	Rapidly Accelerated Fibrosarcoma
RANO	Response Assessment In Neuro-Oncology
RECIST	Response Evaluation Criteria In Solid Tumors
RR	Respiratory Rate
SAE	Serious Adverse Event
SAP	Statistical Analysis Plan
SOC	System Organ Class
T3	Triiodothyronine
T4	Tetraiodothyronine
TEAE	Treatment-Emergent Adverse Event
TRAE	Treatment-Related Treatment-Emergent Adverse Event
TSH	Thyroid Stimulating Hormone
TTR	Time To Response
WHO	World Health Organization

## **1. INTRODUCTION**

DAY101-102a is a Phase 2, multi-center, open-label sub-study of tovotafenib (DAY101) as a monotherapy in patients  $\geq 12$  years of age with recurrent or progressive melanoma or solid tumors with activating BRAF fusion or CRAF/RAF1 fusions or amplification.

The statistical analysis plan (SAP) contains a detailed description of the data presentations and statistical analyses that will be included in the clinical study report for Protocol DAY101-102a. The statistical methods and analyses described here are based on those presented in the Study DAY101-102 Master Protocol Amendment 2 (dated 13 October 2022) and Study DAY101-102a Monotherapy Subprotocol Amendment 2 (dated 19 October 2022).

## 2. STUDY SUMMARY

### 2.1. Study Objectives

The primary objective is:

- To evaluate the efficacy of tovorafenib by RECIST version 1.1 or an alternative appropriate tumor response criteria.

The secondary objectives are:

- To assess the safety and tolerability of tovorafenib.
- To assess additional efficacy parameters of tovorafenib.
- To characterize the tumor responses observed with tovorafenib.
- To characterize the pharmacodynamic (PD) effects of tovorafenib.

The exploratory objectives are:

- To evaluate the genomic profile of archival tumor or fresh tumor biopsies from patients who will be treated with tovorafenib.
- To characterize pathway modulation and/or genomic alterations from tumor biopsies and/or ctDNA.
- [REDACTED]

### 2.2. Study Design

This is an open-label, multicenter, Phase 2 sub-study to evaluate tovorafenib as a monotherapy in patients  $\geq 12$  years of age with recurrent or progressive melanoma or solid tumors with activating BRAF fusion or CRAF/RAF1 fusions or amplification. Molecular assays performed at certified laboratories will be used to identify patients with these alterations. Patients will be enrolled in two separate cohorts: melanoma cohort or tissue agnostic cohort.

Adult patients ( $\geq 18$  years) will receive tovorafenib at 600 mg orally once weekly. For patients ages 12 to  $<18$  years, tovorafenib will be administered at a dose of 420 mg/m^2 (not to exceed 600 mg) orally once weekly. Cycles will repeat every 28 days until radiographic evidence of disease progression, unacceptable toxicity, patient withdrawal of consent, or death.

Patients will undergo radiographic evaluation of their disease at baseline, and then at the end of [REDACTED] for 1 year, and then [REDACTED] thereafter.

A response assessment will be performed according to RECIST version 1.1 for solid tumors or an alternative criteria may be used in specific disease settings, such as glioma, where response assessment will be evaluated by Response Assessment in Neuro-Oncology (RANO) criteria.

Patients who have radiographic evidence of disease progression may be allowed to continue on tovorafenib if, in the opinion of the Investigator, the patient is deriving clinical benefit from continuing study treatment, and continuation of treatment is approved by the Sponsor.

### **2.2.1. End of Study and Length of Study**

The end of study is expected to occur 25 months after the last patient is enrolled. In addition, the Sponsor may decide to terminate this study at any time.

The total length of this study, from screening of the first patient to the end of study, is expected to be approximately 4 years.

On 03NOV2023, the sponsor announced the early termination of this study due to a change in clinical development priorities. As a result, all patients who have not ended the study will end study after being followed for at least 6 months after the first dose of the study drug. The originally planned interim analysis and primary analysis will not be performed. Instead, the final analysis will be conducted after all patients have ended the study and the data have been cleaned and finalized.

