7.3.1. Efficacy Analyses

The efficacy analyses will be performed on the full analysis set (FAS) population which includes all patients who received at least 1 dose of study drug and have measurable disease as determined by the Investigator at baseline and have at least 1 follow-up imaging or radiographically confirmed progressive disease prior to the first imaging timepoint.

ORR as assessed by the proportion of patients with the best overall confirmed response of CR or PR, according to the appropriate tumor response criteria as assessed by Investigator will be calculated and an exact CI will be calculated. DOR in patients with best overall response of CR or PR as determined by the treating Investigator defined as from time of first tumor response to progression or date of data analysis, whichever occurs earlier will be calculated. PFS is defined as the time from the date of the first dose of study drugs to the first occurrence of disease progression according to the appropriate tumor response criteria as

assessed by Investigator, or death from any cause, whichever occurs earlier. OS is defined as the period from the date of the first dose of study drugs until the date of death from any cause. Kaplan-Meier curves will be plotted for DOR, PFS, and OS. TTR in patients with best overall response of CR or PR will be determined by the treating Investigator from the initiation of study treatment to the date of first response. The timepoint for the analysis of response for Phase 2 studies' primary efficacy objective will be when all patients have a minimum of 6 months of follow-up.

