**Table 2: Schedule of Events**

Assessment	
Informed consent/ assent b	
Demographics	
Medical History	
ECOG or Lansky (for patients <16 years of age)	
Physical examination c	
Neurologic Examination d	
Dermatologic Examination d	
Bone Age e	
Tanner Staging f	
Vital signs g	
12-lead ECG in triplicate g	
Hematology h	
Chemistry h	
Creatine phosphokinase h	
Coagulation Panel (APTT/INR) i	
Thyroid function test i	
HBcAb, HBsAg, HCV RNA j	
HIV-1 Ab, HIV-2 Ab, HIV viral load and CD4+ T cell count j	
Echocardiogram/MUGA k	
Ophthalmologic exam l	
Visual symptom assessment m	
Pregnancy test n	
Adverse events o	

Assessment	
Concomitant medication p	
Tumor assessment CT/MRI q	
Archival tumor tissue samples r	
Freshly acquired tumor tissue sample (PD analysis) s,t	
PK Sample u, v	
ctDNA v	
Additional anticancer treatment and survival status w	
Tovorafenib dosing x	
Tovorafenib Drug Dosing Diary y	
Tovorafenib drug Dispensation/Return z	

a Results of screening assessments must be reviewed by Investigator before patient enrollment to confirm that the patient meets the eligibility criteria.

b Informed consent may be obtained greater than [REDACTED] but must be provided before any study-specific procedures are performed; however, evaluations performed as part of routine care prior to informed consent can be utilized as screening evaluations if permitted by site IRB/IEC policies.

Assessments will be performed at the end of [REDACTED]

[REDACTED]. Assessments are to be performed on or up to 7 days before the next cycle. For CT/MRI, assessments are to be performed per the protocol-defined schedule regardless of whether study treatment is discontinued. To ensure image consistency, the same imagine modalities and acquisition protocols used at Screening are to be used for subsequent tumor assessments.

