##### **3.1.2. Reporting of Numerical Values**

Relevant descriptive statistics (n, mean, standard deviation, median, minimum, and maximum) will be calculated for continuous variables. Confidence intervals (CIs) will be provided where appropriate.

Frequencies and percentages will be presented for categorical and ordinal variables, with the frequencies reported as integers and percentages reported with one decimal place. Unless otherwise specified, the percentages will be calculated based on the total number of patients included for the analysis group. Frequencies and percentages for patients with missing data may be presented.

Means, medians, and confidence intervals will be reported to one decimal place more than the data reported on the case report form (CRF) or by the laboratory/vendor. Standard deviations will be reported to two decimal places more than the data.

A month is operationally defined to be 30.4375 days. Six months is operationally defined to be 182.625 days. One year is defined to be 365.25 days.

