### **3.3. Analysis Variables**

#### **3.3.1. Primary Efficacy Variable**

##### **3.3.1.1. Overall Response Rate**

The primary efficacy variable is overall response rate (ORR) defined as the proportion of patients with the best overall confirmed response of complete response (CR) or partial response (PR) according to the appropriate response assessment criteria for the disease setting as assessed by the Investigator.

Complete or partial responses will be recognized if the criteria for each are met at a subsequent scan, a minimum of 4 weeks later.

Guidance on the determination of best overall confirmed response by RECIST 1.1 and RANO response criteria are provided in Section [6.1](#) and [6.2](#) of the Appendix.

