## 6. APPENDIX

### 6.1. Best Overall Assessment by RECIST 1.1

Overall Response First Time Point	Overall Response Subsequent Time Point	Best Confirmed Overall Response
CR	CR	CR
CR	PR	PR a , SD, PD
CR	SD	SD provided minimum criteria for SD duration met, otherwise, PD
CR	PD	SD provided minimum criteria for SD duration met, otherwise, PD
CR	NE	SD provided minimum criteria for SD duration met, otherwise, NE
PR	CR	PR
PR	PR	PR
PR	SD	SD
PR	PD	SD provided minimum criteria for SD duration met, otherwise, PD
PR	NE	SD provided minimum criteria for SD duration met, otherwise, NE
NE	NE	NE

Abbreviations: Abbreviations: CR, complete response; NE, not all evaluated; PD, progressive disease; PR, partial response; SD, stable disease.

a If a CR is truly met at first time point, then any disease seen at a subsequent time point, even disease meeting PR criteria relative to baseline, makes the disease PD at that point (since disease must have reappeared after CR). Best response would depend on whether minimum duration of 8 weeks for SD was met. However, sometimes 'CR' may be claimed when subsequent scans suggest small lesions were likely still present and in fact the patient had PR, not CR at the first time point. Under these circumstances, the original CR should be changed to PR and the best response is PR.

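### After early termination, patients may leave at 6 months with a response still awaiting its 4-week confirmation, so confirmed ORR may be biased low and the SAP has no rule or supportive analysis for such responses

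*SAP*

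**What the plan says.** SAP 2.2.1 records the termination announced on 3 November 2023. It states that patients who have not yet ended the study "will end study after being followed for at least 6 months after the first dose of the study drug"; SAP 2.3.3 repeats this. The interim and primary analyses are cancelled and one final analysis remains. SAP 3.1.2 fixes the unit: "Six months is operationally defined to be 182.625 days".

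SAP 3.3.1.1 defines the primary variable as confirmed ORR by Investigator assessment: "Complete or partial responses will be recognized if the criteria for each are met at a subsequent scan, a minimum of 4 weeks later". SAP 3.7.1 applies the same rule. It plans exact 95% confidence intervals and a breakdown by best overall response, with no line for unconfirmed responses.

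On scan timing, cycles last 28 days (SAP 2.2) and a Table 2 footnote says: "Assessments are to be performed on or up to 7 days before the next cycle". The scan interval itself is redacted. Tumor assessments continue on schedule after treatment stops (SAP 2.3.6), but under Protocol 6.26 long-term follow-up ends when the study is closed.

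On coding, SAP 6.1 assigns a CR or PR followed by an NE assessment to "SD provided minimum criteria for SD duration met, otherwise, NE", and its footnote gives 8 weeks as the minimum duration for SD. No row covers a first response with no later scan. SAP 6.2 (RANO) contains no confirmation table.

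Before termination, Protocol 7.3.1 already placed the response analysis at the time that "will be when all patients have a minimum of 6 months of follow-up", and SAP 2.3.2 used a similar minimum. The study was then expected to run until 25 months after the last enrolment.

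**The concern.** The exit rule and the endpoint definition do not refer to each other. A patient may leave from 182.625 days, while a response seen in the last 4 weeks before exit needs a scan after exit to count. If that scan is lost, the cause is the sponsor's closure and not failure of the response.

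Any effect on confirmed ORR can go only one way, because a pending response can be lost but none can be gained. It falls on patients closed out near the minimum, so the estimate would partly reflect closure timing. Under SAP 3.2.1 only confirmed responders are evaluable for DOR and time to response, so a pending responder also drops out of those summaries. A reader of the final table could not tell such a patient from one whose tumor never responded.

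**Working it through.** **Inputs.** Month 30.4375 days and six months 182.625 days (SAP 3.1.2); confirmation interval 28 days (SAP 3.3.1.1, 3.7.1); cycle 28 days (SAP 2.2); scan on the first day of the next cycle or up to 7 days before it (SAP Table 2 footnote). Scan interval, cohort sizes and response hypotheses are redacted.

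**Plan's own figure.** 6 × 30.4375 = 182.625 days, which agrees with SAP 3.1.2.

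**Latest confirmable first response at the minimum.** 182.625 − 28 = 154.625 days after first dose, or 154.625 / 7 = 22.1 weeks. This step needs no assumption about the scan schedule.

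**If there is an end-of-Cycle-6 scan (assumption).** Cycle 7 would start 6 × 28 = 168 days after first dose, so the scan falls 161 to 168 days after first dose. SAP 3.1.7.1 counts the first dose as day 1, which makes these study days 162 to 169.
- Earliest confirmation: 161 + 28 = 189 to 168 + 28 = 196 days after first dose, which is study days 190 to 197.
- Shortfall of the minimum: 189 − 182.625 = 6.4 days to 196 − 182.625 = 13.4 days.
- A scan done at exit on day 182.625 would be only 14.6 to 21.6 days after the Cycle 6 scan, too soon to confirm.

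**Other assumed schedules.** Scans every 1, 2, 3 or 6 cycles all include week 24 and show this gap. Scans every 4 cycles do not. A week-16 response would then next be scanned on schedule at week 32 (day 224), again after the minimum, although an unscheduled scan from day 112 + 28 = 140 could confirm it.

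**Share of responses exposed, for a patient leaving at the minimum (assumption-based).** Assume the 10.5-week median time to response in Protocol 1.3.4 and scans every k weeks. The share of responses seen by week 24 that are first seen at week 24 is [F(24) − F(24 − k)] / F(24).

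| Scan interval | Exponential | Gamma, shape 3 |
|---|---|---|
| 4 weeks | 0.0620 / 0.7949 = 7.8% | 0.0599 / 0.9429 = 6.3% |
| 8 weeks | 0.1427 / 0.7949 = 17.9% | 0.1702 / 0.9429 = 18.1% |
| 12 weeks | 0.2478 / 0.7949 = 31.2% | 0.3536 / 0.9429 = 37.5% |

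**Effect on ORR (illustrative).** Let q be that share and e the fraction of such patients who leave before confirmation. Assume late responses would be confirmed as often as earlier ones. Observed ORR = ORR × (1 − q × e). With an assumed ORR of 30%:
- e = 0: 30%.
- e = 25%: 0.30 × (1 − 0.063 × 0.25) = 29.5% to 0.30 × (1 − 0.375 × 0.25) = 27.2%.
- e = 100%: 0.30 × (1 − 0.063) = 28.1% to 0.30 × (1 − 0.375) = 18.8%.

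The value of e is not in the documents.

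**Cost of one lost response.** 100 / N points: 10 at N = 10, 5 at N = 20, 2.5 at N = 40 (assumed sizes).

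**The case against.** The strongest reply is that six months is a minimum, not an exit day. The text already permits a site to wait for a confirming scan, and nothing shows that any patient left with a response pending. That stands. A reader might infer that responses are in fact being lost and that ORR is biased low; the documents show only that this can happen.

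The planned primary analysis used the same minimum, so a late responder among the last patients enrolled could have been unconfirmed at that cut as well. This also stands. What termination removes is the follow-up beyond that cut, during which a pending response could have been resolved before the end of the study.

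Three further readings go too far:
- That a week-24 scan is part of the schedule. The interval is redacted; only the day-154.6 limit is independent of it.
- That the SAP codes these patients as SD. The PR-then-NE row is the nearest fit, but it describes a later assessment rated NE, not an absent one, and RANO has no rule.
- That each such case is a true response. Under the confirmed definition a single scan is not yet a response, and some would not have been confirmed.

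A reader might also cite the unconfirmed PR in Protocol Table 1. The footnote says its confirmation scan had not been read by the independent committee, in another study, so it does not illustrate loss through closure.

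On timing, the SAP was approved on 11 and 12 April 2024. A patient first dosed on the announcement date reaches six months about 3 May 2024, so extended follow-up may help few patients. The supportive analysis does not depend on that. Patient listings will show pending responses, but they do not give an ORR that includes them.

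**Conclusion.** The gap holds on the SAP's own text. In a patient closed out at 182.625 days, a CR or PR first seen after about day 154.6 cannot be confirmed and counts as a non-response, and no SAP provision covers it. Confirmed ORR may be biased low; it cannot be biased high by this route.

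The size cannot be determined. It depends on the redacted scan schedule and on how many patients leave near the minimum with a response pending, which may be none. The 6% to 38% shares apply only to patients leaving at the minimum. They rest on an assumed time-to-response distribution whose median comes from a small group of glioma patients (five responders among eight with a RAF fusion), not from melanoma or tissue-agnostic cohorts. The coding gap in SAP 6.1 and 6.2 leaves ORR itself unchanged but makes the SD, not-evaluable and missing counts ambiguous.

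The change is worth making because it is cheap and lets a reader separate closure from drug effect.

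**What to change.** 1. **SAP 3.7.1:** keep confirmed ORR as primary. Add a supportive row by cohort with the number of CR/PR that are unconfirmed solely because of study closure, and the ORR with exact 95% CI including them. This uses data already collected and costs one table row.
2. **SAP 6.1 and 6.2:** state the best-overall-response category for a first CR or PR with no later scan, under both RECIST 1.1 and RANO. This costs a line of text in each.
3. **SAP 2.2.1 and 2.3.3, for patients still on study:** let a patient with a pending CR or PR remain in follow-up until the next scheduled tumor assessment at least 4 weeks after the first response. This concerns follow-up imaging only. The cost is a possible delay to database lock until that scan. If the assumed Cycle 6 scan exists, the next scheduled scan falls 189 to 196 days after first dose with scans every cycle, 217 to 224 with every second cycle, or 245 to 252 with every third.

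If all patients have already left, items 1 and 2 can still be done in full.
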